## 2. STUDY DETAILS

### 2.1 Study Objectives

#### Primary:

1. To compare the impact of vaccination with *Na*-GST-1/Alhydrogel® delivered with or without AP 10-701 or CpG 10104 on controlled human hookworm infection (CHHI) with *N. americanus* larvae in healthy, hookworm-naïve adults, as determined by the presence of eggs using a qualified flotation technique.
2. To evaluate the safety and reactogenicity of *Na*-GST-1/ Alhydrogel® delivered with or without AP 10-701 or CpG 10104 on Days 0, 56 and 112, in healthy, hookworm-naïve adults.

#### Secondary:

1. To compare the impact of vaccination with *Na*-GST-1/Alhydrogel® delivered with or without AP 10-701 or CpG 10104 on fecal egg counts, as determined by the McMaster method, after controlled human hookworm infection (CHHI) with *N. americanus* larvae in healthy, hookworm-naïve adults.
2. To assess the relationship between antibody responses to *Na*-GST-1 induced by vaccination with *Na*-GST-1/Alhydrogel® delivered with or without AP 10-701 or CpG 10104 and responses to CHHI in healthy, hookworm-naïve adults, as determined by the presence of eggs using a qualified flotation technique.
3. To assess the duration of antibody responses to *Na*-GST-1 induced by vaccination with *Na*-GST-1/Alhydrogel® delivered with or without AP 10-701 or CpG 10104.
4. To assess the impact of vaccination with *Na*-GST-1/Alhydrogel® delivered with or without AP 10-701 or CpG 10104 on the affinity of antibody-antigen interactions, and how affinity relates to responses to CHHI in healthy, hookworm-naïve adults, as determined by the presence of eggs using a qualified flotation technique.
5. To assess the relationship between *Na*-GST-1 specific memory B cells induced by vaccination with *Na*-GST-1/Alhydrogel® delivered with or without AP 10-701 or CpG 10104 and responses

to CHHI in healthy, hookworm-naïve adults, as determined by the presence of eggs using a qualified flotation technique.

6. To assess the relationship between innate immune responses to *Na*-GST-1/Alhydrogel® delivered with or without AP 10-701 or CpG 10104 and responses to CHHI in healthy, hookworm-naïve adults.

### **Exploratory:**

1. To assess the relationship between the functional capacity of vaccine-induced antibodies that neutralize the in vitro activity of native *Na*-GST-1 enzyme and responses to CHHI in healthy, hookworm-naïve adults.
2. To compare the impact of vaccination with *Na*-GST-1/Alhydrogel® delivered with or without AP 10-701 or CpG 10104 on levels of hookworm DNA as detected by real-time PCR in healthy, hookworm-naïve adults challenged with CHHI, as determined by the presence of eggs using a qualified flotation technique.

### **2.2 Study Design**

The study will be a randomized, double blind, placebo-controlled Phase 2 clinical trial in healthy hookworm-naïve adult subjects. This study is designed to evaluate the efficacy, safety, reactogenicity, and immunogenicity of *Na*-GST-1/Alhydrogel® administered with or without the point-of-injection addition of the immunostimulants AP 10-701 or CpG 10104. To assess the impact of vaccination with these different vaccine formulations on infection, subjects will be challenged with 50 infectious *N. americanus* larvae by controlled human hookworm infection (CHHI) 4 weeks after the 3rd vaccination. Safety parameters will be monitored throughout the study.

Subjects will be invited to participate in the study by means of verbal and email announcements and poster, newspaper, and online advertisements. After providing written informed consent, subjects will undergo eligibility screening, including a complete medical history; physical examination; hematology testing; liver and renal function testing; anti-double stranded DNA (anti-dsDNA) and rheumatoid factor (Rf) testing; Human Immunodeficiency Virus (HIV), Hepatitis B, and C testing; fecal occult blood testing; fecal examination for ova and parasites; and, urinalysis (for protein and glucose). Urine pregnancy testing will be performed on all female subjects. All clinically significant abnormalities will be reviewed with subjects and they will be referred for follow-up care if appropriate. After screening, those subjects determined to be eligible, based on the inclusion and exclusion criteria described in Section 5 in the study protocol, will be invited to participate in the study. No exemptions from the inclusion or exclusion criteria will be granted on inclusion/exclusion.

In the study, 48 subjects will be enrolled and randomized into 4 groups. Groups will not be enrolled separately; rather, eligible subjects will be randomly assigned to a group upon enrollment in a double-blind fashion (i.e., neither the subject nor the investigators will know to which group the subject has been assigned). In the first group (n=12), subjects will receive 100µg *Na*-GST-1/Alhydrogel®. In the second group (n=12), subjects will receive 100µg *Na*-GST-1/Alhydrogel® co-administered with 500µg CpG 10104. In the third group (n=12), subjects will receive 100µg *Na*-GST-1/Alhydrogel® co-administered with 5µg AP 10-701. In the fourth group (n=12), subjects will receive sterile saline placebo.

Subjects will be followed until 10 months after their final vaccination, for a total of 14 months of study participation. See Appendix A of protocol for a detailed description of the scheduled clinical and laboratory evaluations during the Vaccination and CHHI phases of the trial.

The table below shows the detail of study Schedule of Events for Vaccination and CHHI Phase:

CONFIDENTIAL

Table 1: Schedule of Events – Vaccination Phase

Study Day		Pre 	0	3 (±1)	7 (±2)	14 (±2)	28 (±4)	56 (±7)	59 (±1) 	63 (±2) 	70 (±2) 	84 (±4) 	112 (±7) 	115 (±1) 	119 (±2) 	126 (±2) 
Visit Number		Pre 	1	2	3	4	5	6	7	8	9	10	11	12	13	14
Blood Volume	Procedures															
	Complete History/Physical	X														
	Obtain Informed Consent	X														
	Interim Clinical Evaluation		X	X	X		X		X	X			X		X	X
	Telephone call			X			X		X			X			X	
	Urinalysis	X														
	Urine pregnancy test (females)	X	X					X					X			
2 mL	CBC 	X	X			X		X			X		X			X
5 mL	RF, anti-dsDNA	X	X			X		X			X		X			X
	Serum ferritin	X														
5 mL	ALT	X	X			X		X			X		X			X
	Creatinine	X	X			X		X			X		X			X
10 mL	HCV testing	X														
	HBsAg testing	X														
	HIV testing	X														
	Fecal sample collection	X														X
	VACCINATION		1					2					3			
10 mL	Anti-Na-GST-1 antibody assays	X			X		X			X		X				X
50 mL	Innate & Cellular immunity assays	X		X	X		X		X	X		X			X	X
	Blood Volume (mL)	22	72		50	72		72		50	72		72		50	72
	Total Blood Volume (mL)	22	94		144	216		288		338	410		482		532	604

Completed within 90 days of first vaccination.

CBC parameters to be assessed for safety: WBC, absolute neutrophil count, absolute eosinophil count, hemoglobin, and platelet count.

Since Vaccination #2.

Since Vaccination #3.

CONFIDENTIAL

George Washington University  
 Statistical Analysis Plan  
 Version Final 1.0

Private and Confidential  
 Study Code: SVI-CH-02  
 Date: JUN 15, 2020

Table 1: Schedule of Events – CHHI Phase

Study Day		140 (±7) 	143 (±1) 	147 (±2)	154 (±2)	175 (±3)	182 (±3)	189 (±3)	196 (±3)	203 (±3)	210 (±3)	217 (±3)	224 (±3)	231 (±3)	238 (±3)	245 (±3)	252 (±3)	259 (±3)	266 (±3)	273 (±3)	280 (±3)	290 (±3)	294 (±3)	297 (±3)	320 (±14)	380 (±14)
Visit Number		15	16	17	18	19	20	21	22	23	24	25	26	27	28	29	30	31	32	33	34	35	36	37	38	39
Blood Volume		Procedures																								
Interim Clinical Evaluation		X	X	X	X	X	X	X	X	X	X	X	X	X	X	X	X	X	X	X	X	X	X	X	X	
Telephone Call								X	X	X	X	X	X	X	X	X	X	X								
2 mL		CBC 	X		X	X	X	X	X	X	X	X	X	X	X	X	X	X	X						X 	
5 mL		ALT, Creatinine	X		X																					
5 mL		RF, anti-dsDNA																								X
Urine pregnancy test (females)		X																			X			X		
LARVAL INOCULATION		X																								
Fecal sample collection 				X	X	X	X	X	X	X	X	X	X	X	X	X	X	X	X	X	X	X	X	X	X	
10 mL		Antibody assays	X		X	X	X	X													X			X	X	X
50 mL		Innate & cellular immunity assays	X		X	X	X														X			X		
Anthelmintic Rx																					X					
Blood Volume (mL)		67	10	67	62	62	2	2	62	2	2	62	2	2	62	2	62	15	10							
Total Blood Volume (mL)		671	681	748	810	872	874	876	938	940	942		1004					1066	1081	1091						

CBC parameters to be assessed for safety: WBC, absolute neutrophil count, absolute eosinophil count, hemoglobin, and platelet count.

Subjects with laboratory evidence of eosinophilia post-larval inoculation only.

Subjects that withdraw from the study prior to study Day 280 will be strongly encouraged to provide post-treatment fecal samples to ensure cure of the infection.

Since Vaccination #3.

Since Larval Inoculation.

CONFIDENTIAL

### 3. DATA ANALYSIS CONSIDERATIONS

#### 3.1 Determination of Sample Size

Sample size considerations are based on the proportion of subjects with detectable hookworm eggs at any time, as measured by the saturated saline flotation technique. The primary analysis will consist of comparing the proportion of subjects in each of the three *Na*-GST-1 vaccination groups (groups 1, 2 and 3) to the proportion of subjects in the placebo control group (group 4) using a two-sided Fisher exact test, for a total of three comparisons. Targeting a rate of 90% subject hookworm infection as observed in the 50 *Na*-L3 dose cohort and a greater than 80% rate of protection in at least one of 3 vaccination groups (e.g., different doses or adjuvant formulations) compared to controls that did not receive the hookworm vaccine, a sample size of 48 (12 per group) would be sufficient to demonstrate the efficacy of a prophylactic hookworm vaccine such as *Na*-GST-1 or *Na*-APR-1, with alpha ~ 0.1 and power of at least 80% [[name] et al, OFID, April 2018].

#### 3.2 Randomization

Eligible subjects will be asked to come to the clinic on their scheduled day of enrolment into the study (Day 0). After undergoing a clinical interview and directed physical examination to ensure that they remain eligible for participation in the study, that they have had blood collected for safety clinical laboratory and baseline immunogenicity assessments, and that females have had a negative urine pregnancy test, subjects will be randomized and enrolled in the order that they present for vaccination.

Within each group, randomization will be done through use of a randomization code using SAS software (Version 9.3 or higher), furnished to the study vaccine manager by the study statistician. Access to the randomization list will be exclusively limited to the study vaccine manager and assistant. Between vaccination days, the randomization list will be stored in a locked cabinet in the GW MFA Investigational Drug Service pharmacy or the office of the study vaccine manager. The study vaccine manager and assistant will be unblinded but will not be involved in further evaluation of study subjects or assessment of adverse events. Subjects will not be considered enrolled in the study until they have received their first dose of vaccine. In the event that a subject is randomized but not enrolled on the day of first vaccination, they will be replaced with an eligible alternate. Enrolled subjects that leave the study for any reason following first vaccination will not be replaced.

Vaccine/placebo assignment will be done by block randomization. That is, for each block of 4 subjects who are sequentially enrolled into the trial, 1 will be assigned to receive *Na*-GST-1/Alhydrogel®, 1 to *Na*-GST-1/Alhydrogel® plus CpG 10104, 1 to *Na*-GST-1/Alhydrogel® plus AP 10-701, and 1 to sterile saline placebo.

#### 3.3 Blinding

Due to the double-blind nature of this Phase 2 clinical trial, neither study subjects nor study team personnel will know to which group an individual subject has been assigned. Investigators and subjects will be blinded to the vaccine/placebo allocation until all subjects have completed their final study visit (i.e., Visit #39 at Day 380), the primary (efficacy and safety) and secondary IgG immunogenicity outcomes (i.e., anti-*Na*-GST-1 IgG antibody results by ELISA) have been monitored and entered into the database, and the database has been locked for analysis.

The study vaccine manager will also prepare all investigational product doses (vaccine or sterile saline placebo) in a separate room and will hand filled syringes to the vaccinator(s). Since the doses of the *Na*-GST-1 formulations are of different opacity than that of sterile saline (slightly turbid vs. clear, respectively), the contents of all syringes will be disguised using opaque tape. As a further precaution, the vaccinator(s) will not be involved in assessments of reactogenicity or adverse events.

#### **4. PRIMARY AND SECONDARY ENDPOINTS**

##### **4.1 Primary Outcome Measures**

The following parameters will be evaluated for each formulation of *Na*-GST-1, in comparison to the saline placebo control:

1. Proportion of subjects with detectable hookworm eggs, at any time point, in fecal samples, as determined by microscopy using the qualified saline flotation technique.
2. Frequency of solicited injection site and systemic reactogenicity, graded by severity, on the day of each study vaccination through 14 days after each study vaccination.
3. Frequency of solicited adverse events, graded by severity, on the day of CHHI through study Day 280.
4. Frequency of study vaccine-related Serious Adverse Events from the time of the first study vaccination through approximately 10 months after the last study vaccination.
5. Frequency of clinical safety laboratory adverse events.
6. Frequency of unsolicited adverse events, graded by severity, from the time of each study vaccination through approximately 1 month after each study vaccination; and from the time of CHHI through treatment with albendazole (Day 297).
7. Frequency of new-onset chronic medical conditions through approximately 10 months after the third study vaccination.
8. Frequency of Adverse Events of Special Interest through approximately 10 months after the third study vaccination.

##### **4.2 Secondary Outcome Measures**

The following parameters will be evaluated for each formulation of *Na*-GST-1, in comparison to the saline placebo control:

1. Fecal egg counts during Weeks 5 through 20 post-CHHI.
2. The anti-*Na*-GST-1 IgG antibody response (ELISA) at approximately 14 days after each vaccination, and approximately 1, 2, 4, 6, 7, 8 and 10 months after the third dose.

##### **4.3 Exploratory Outcome Measures**

1. The functional capacity of vaccine-induced antibodies to neutralize the in vitro activity of the native *Na*-GST-1 enzyme.
2. Levels of *N. americanus* DNA in fecal samples, as measured by real-time PCR, during Weeks 5 through 20 post-CHHI.

## 5. STATISTICAL METHODOLOGY

### 5.1 General Considerations

The statistical analyses will be performed by Quartesian Clinical Research, using SAS Version 9.3 (or higher). All tables, figures and listings will be produced in landscape format. In general, all data will be listed by the subject and visit/time point where appropriate.

Data will be summarized by time-point where appropriate. The total number of subjects in the study group (N) under the stated population will be displayed in the header of summary tables.

Data will be summarized using descriptive statistics for continuous variables. Unless otherwise stated, descriptive statistics will include number of subjects, mean, standard deviation, minimum, median and maximum for all endpoints in case of  $n < 2$ , where n indicates the number of evaluable subjects at the particular time point, only n, mean, minimum and maximum will be displayed. The statistic "Missing" will also be evaluated by enumerating the number of missing entries/subjects, if any at that visit, and presented along with summary statistic. Display NC if any value is not computable.

Decimal Precision Convention: The minimum and maximum statistics will be presented to the same number of decimal places as the original data. The mean and median will be presented to one more decimal place than the original data, whereas the standard deviation will be presented to two more decimal places than the original data.

For categorical variables, counts and percentages will be used. The count [n] indicates the actual number of subjects with non-missing value at particular visit or actual number of subjects with that event or category, which should always be less than or equal to the total number of subjects in the respective study group [N]. Percentage will be obtained by:  $\% = (n/N) * 100$ .

Unless otherwise stated, all percentages will be expressed to one decimal place.

Also, the distributions for continuous variables will be examined for normality using Shapiro-Wilk tests. If any deviation in the normality assumption is judged, then the data will be analyzed using appropriate non-parametric tests.

The following conventions will be applied to analyses/data presentation:

All dates will be displayed in DDMMYY format.

In general, all data will be listed, sorted by cohort, treatment group, and subject ID, and when appropriate by parameter and then visit number within subject. All summary tables will be structured with a column for each treatment and will be annotated with the total population size relevant to that table/treatment, including any missing observations.

#### Study Hypotheses:

This study is not designed to test statistically significant small differences in efficacy between different adjuvant formulations of the *Na-GST-1* hookworm vaccine as assessed in the CHHI model. Rather, it is intended to provide an indication of an impact on infection as assessed by CHHI, and to detect large differences in efficacy with acceptable power. Furthermore, the study intends to assess the safety, reactogenicity, and immunogenicity of three novel adjuvant formulations of *Na-GST-1*: *Na-GST-1*

formulated on Alhydrogel, *Na*-GST-1/Alhydrogel® administered with AP 10-701, and *Na*-GST-1/Alhydrogel® administered with CpG 10104.

The chosen sample size principally facilitates the assessment of efficacy (as estimated by infection status following CHHI) as well as safety, as discussed in SAP Section 3.1, Sample Size Considerations. Given that, this study will attempt to assess the following hypotheses:

1. Administration of the *Na*-GST-1/Alhydrogel® vaccine with either AP 10-701 or CpG 10104 will result in a reduced proportion of subjects infected with hookworm following CHHI compared to placebo controls.
2. Co-administration of *Na*-GST-1/Alhydrogel® vaccine with either AP 10-701 or CpG 10104 will increase the IgG antibody response to *Na*-GST-1 compared to when *Na*-GST-1/Alhydrogel® is administered alone.
3. Co-administration of *Na*-GST-1/Alhydrogel® vaccine with either AP 10-701 or CpG 10104 will increase the affinity of induced IgG antibodies to *Na*-GST-1 compared to when *Na*-GST-1/Alhydrogel® is administered alone.
4. Co-administration of the *Na*-GST-1/Alhydrogel® vaccine with either AP 10-701 or CpG 10104 will increase the induction of specific MBCs to *Na*-GST-1 compared to when *Na*-GST-1/Alhydrogel® is administered alone.
5. Co-administration of the *Na*-GST-1/Alhydrogel® vaccine with either AP 10-701 or CpG 10104 increases the neutralizing capacity of induced IgG antibodies to *Na*-GST-1 compared to when *Na*-GST-1/Alhydrogel® is administered alone.
6. Co-administration of *Na*-GST-1/Alhydrogel® vaccine with either AP 10-701 or CpG 10104 will increase the avidity of induced IgG antibodies to *Na*-GST-1 compared to when *Na*-GST-1/Alhydrogel® is administered alone.

#### **Protocol Deviations:**

If there are major protocol deviations, a per-protocol (PP) analysis may also be performed. Immunogenicity or parasitology data from any visit that occurs substantially out of window will be reviewed by the Principal Investigator for decisions regarding inclusion or exclusion of the data.

#### **Handling of Missing Data:**

For partial start dates:

1. If the year is unknown, then do not impute the date but assign a missing value.
2. If the month is unknown, then:
  - a. If the year matches the year of the first dose date, then impute the month and day of the dose date.
  - b. Otherwise, assign “January”.
3. If the day is unknown, then:
  - a. If the month and year match the month and year of the first dose date, then impute the day of the dose date.
  - b. Otherwise, assign “01”.

For partial end dates:

1. If the year is unknown, then do not impute the date but assign a missing value.
2. If the month is unknown, then assign “December”.
3. If the day is unknown, then assign the last day of the month.

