### **2.2.2 Rationale for Na-GST-1 Doses and Dose Schedule to be Studied**

For the study proposed in this clinical protocol, each subject will be vaccinated three times, on Days 0, 56, and 112, by intramuscular injection in the deltoid muscle. This vaccination schedule was selected to coordinate with the Expanded Program on Immunization as the human hookworm vaccine is intended to target children, including infants, and it is the schedule that has been tested in all but one of the Phase 1 trials of Na-GST-1, to date. Local subcutaneous nodules, believed to be granulomatous reactions to aluminum hydroxide, have been observed with use of aluminum hydroxide-based adjuvants. Thus, most aluminum hydroxide-adsorbed vaccines are injected intramuscularly (IM) rather than subcutaneously, and intramuscular injection in the deltoid muscle will be used for administration of all investigational products in the study. The doses of Na-GST-1, AP 10-701 and CpG 10104 are the maximum doses that have been tested in the human clinical trials conducted to date, as described above. This is justified since these doses were all well tolerated and there appears to be a dose effect for Na-GST-1 in terms of immunogenicity.

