## 8 STUDY PROCEDURES/EVALUATIONS

### 8.1 Clinical Evaluations

Subjects will be monitored for local and systemic adverse events during specific protocol-defined periods. As with other aluminum hydroxide-adsorbed vaccines, hypersensitivity reactions would be expected to occur within the first 24 hours after vaccination, and other severe local or systemic reactions within 72 hours of vaccination. Subjects will therefore be observed for immediate reactions following each vaccination for at least 1 hour, and will have a clinical assessment at the study clinic on Days 7 and 14 following each vaccination. A telephone call with the subject will take place on Days 3 and 28 following vaccinations 1 and 2 to monitor for adverse events. Day 28 following vaccination 3 falls on the day of CHHI and the subject will be assessed at the study clinic. Should a subject call on a study clinician to report an adverse event (AE), it will be fully documented in their study chart, and discussed with the Principal Investigator.

Following CHHI, local larval application site reactions are expected to occur within the first month after application of the larvae. Subjects will therefore be observed for immediate reactions following each larval application for at least 1 hour. Subjects will have a telephone call on day 3 following CHHI to monitor for adverse events. A clinical assessment at the study clinic will be performed on Days 7 and 14 following CHHI. Gastrointestinal AEs are expected to occur after approximately week 4 after CHHI; subjects will therefore be evaluated weekly from weeks 5 through 20 after CHHI, until treatment with albendazole.

All AEs will be graded for severity and relationship to study vaccine or larval application, captured on the appropriate case report form (CRF), and followed to resolution. All Serious Adverse Events (SAEs) will be reviewed by a study physician, recorded on the appropriate SAE form, reported according to applicable regulations and guidelines, and followed through to resolution or stabilization by a study clinician. Special attention will also be paid to monitoring for the occurrence of Adverse Events of Special Interest (AESIs), which include inflammatory and autoimmune disorders that may potentially be related to the use of an immunostimulatory adjuvant, and gastrointestinal, hematologic or respiratory disorders that may potentially be related to CHHI.

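### Partial start dates are anchored on the first dose only, so a partially dated adverse event can be dated before the later vaccination or larval challenge it followed

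*SAP*

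**What the plan says.** SAP 5.1 has one set of rules, headed "For partial start dates". It does not name adverse events but covers them, because it covers every start date. For an unknown day: "If the month and year match the month and year of the first dose date, then impute the day of the dose date"; in any other month the day is set to the 1st. For an unknown month: "If the year matches the year of the first dose date, then impute the month and day of the dose date"; in any other year the month is set to January. No rule mentions dose 2, dose 3 or CHHI, and nothing else in the SAP says how a partially dated event is assigned to an exposure.

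The trial has four exposures. Protocol 2.2.2 says that "each subject will be vaccinated three times, on Days 0, 56, and 112", and protocol 8.1 says that "Day 28 following vaccination 3 falls on the day of CHHI", which makes challenge Day 140.

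Several summaries depend on which exposure an event followed:
- SAP 4.1, item 6, counts unsolicited events "from the time of each study vaccination through approximately 1 month after each study vaccination", and then from challenge to Day 297. Protocol 9.1, item 5, puts the vaccination windows at about 28 days.
- SAP 5.7.5.1 summarises adverse events by vaccination.
- SAP 5.7.5.2 tabulates post-vaccination events on the Safety Population, and SAP 5.7.5.3 tabulates post-challenge events on the Per-protocol Population.

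**The concern.** Anchoring on the first dose is a sound convention for a trial with one exposure, since it stops an event that followed treatment from being dated before it. Here it protects the first boundary and leaves three unprotected. An event with unknown day in the month of dose 2, dose 3 or challenge goes to the 1st of that month, usually before that exposure. An event with unknown month in the first-dose year goes to Day 0, even if it followed challenge.

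At stake is attribution. An event after dose 2 or 3 can land between windows, where a programmer must leave it unassigned or attach it to the previous dose. A challenge event can land in the dose 3 window and so change phase, table and denominator, because the two phases use different populations. With 12 subjects per arm, one displaced subject changes a group frequency by 1/12 = 8.3 percentage points. The SAP states a rule here, and the rule gives wrong dates; this is not simply missing detail.

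**Working it through.** The plan gives no figure to reproduce, so the check applies the SAP rules as written.

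**Inputs.** Exposures on Days 0, 56, 112 and 112 + 28 = 140 (protocol 2.2.2 and 8.1). Unsolicited-event windows are Days 0-28, 56-84, 112-139 and 140-297 (protocol 9.1, with Day 140 counted as challenge), so the last three hold W = 29, 28 and 158 days. Assumptions: nominal visit days, every onset day in a window equally likely, and every first-dose date in a four-year calendar (1,461 dates, one leap year) equally likely.

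**Unknown day.** Suppose the exposure falls on day x of a month with L days. Onsets later in that month are set to the 1st, which precedes the exposure unless x = 1. Onsets in later months go to the 1st of those months, after the exposure. So min(W, L - x + 1) onset days are moved when x ≥ 2, and none when x = 1. Four years contain 28 months of 31 days, 16 of 30, 3 of 28 and 1 of 29. Summing over x for each month length:

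- Dose 2 (W = 29): 464, 435, 378 and 406 for L = 31, 30, 28 and 29. Total 28×464 + 16×435 + 3×378 + 406 = 21,492, out of 1,461×29 = 42,369: **50.7%**.
- Dose 3 (W = 28): 462, 434, 378 and 406. Total 21,420, out of 1,461×28 = 40,908: **52.4%**.
- CHHI (W = 158): 465, 435, 378 and 406. Total 21,520, out of 1,461×158 = 230,838: **9.3%**.

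For onsets within Days 0-14 after any of these three exposures, the share is 73.7%.

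**Where the moved events land.** For doses 2 and 3, 99% fall in Days 29-55 or 85-111, in no window, and 1% in the previous dose's window. For CHHI, 99.5% fall in the dose 3 window.

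**Unknown month.** Every event in the first-dose year is set to Day 0. In another year I take the result as 1 January, since the unknown-day rule supplies the 1st. Over all first-dose dates, 95.9% (dose 2), 96.0% (dose 3) and 78.2% (CHHI) move before their exposure. Of those moved, 92%, 76% and 61% land in the dose 1 window.

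**Illustration.** First dose 20 March 2019, dose 2 on 15 May, onset 17 May (Day 58) with the day unknown: imputed 1 May, Day 42, in no window. Challenge on 7 August, onset 9 August (Day 142): imputed 1 August, Day 134, in the dose 3 window.

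**Test of a simple alternative.** Anchoring an unknown day on the latest exposure in the same month moves nothing before doses 2, 3 or CHHI. But it puts 52% of day-missing dose 3 window events into the CHHI window, because challenge follows dose 3 by only 28 days. The known month alone cannot separate these two exposures.

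**The case against.** The strongest reply is that the rule will rarely be used and does little when it is. Subjects are contacted on Days 3, 7, 14 and 28 after each dose and weekly in Weeks 5 to 20 after challenge (protocol 4 and 8.1). Missing data are queried to the site (protocol 13). Solicited events come from memory aids with fixed periods. An unknown month is hard to imagine under that schedule. The eCRF, which is not among the documents, may record phase or vaccination.

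Most primary safety outcomes are also not counted per exposure. Vaccine-related serious events, special-interest events and new-onset chronic conditions run to about 10 months after the last dose, and laboratory events have no per-dose window. SAP 5.7.5.1 counts any event from first dose to last procedure, so overall tables do not change. The rule takes no account of arm.

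All of this stands, and it limits the size and reach of the problem. It does not make the rule right for unsolicited events, which are counted by exposure. If the eCRF does hold a phase field, the SAP does not tell the programmer to use it.

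**Conclusion.** The point holds in limited form. For a partially dated adverse event, the first-dose anchor can give a start date before the exposure that the event followed. With only the day missing, this affects about 51% of dose 2, 52% of dose 3 and 9% of CHHI window events. These are shares of partially dated events, not of all events, and they rest on nominal visit days and uniform onset. The number of partial dates is not given and is probably small. The effect is confined to per-vaccination and per-phase summaries, mainly of unsolicited events.

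Four stronger readings are tempting but not supported:
- **Events are lost.** No SAP rule deletes an event by its imputed date. It may be left unassigned or attached to the previous dose.
- **An imputed start can fall after a known stop.** Not for adverse events: each current rule returns a date on or before any true onset after dose 1. It could happen only for items that began before dose 1, such as prior medications.
- **About 94% of events are misdated.** That share applies only to onsets in the same calendar month as the exposure, where the 1st precedes the exposure almost by construction.
- **The safety outcomes as a whole, or the comparison between arms, are biased.** Most of those outcomes have no per-exposure window, and the documents show no difference by arm.

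**What to change.** Replace the start-date rule, for adverse events, with two steps.

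1. **Assign the exposure.** Use the recorded study phase or vaccination where available. Otherwise take the latest exposure given strictly before the visit or contact at which the event was first reported. An event reported at the Day 140 visit before larval application then belongs to dose 3. An exposure later than the last date allowed by the known part of the start date, or by a known stop date, is not a candidate.
2. **Impute the date.** Use the later of that exposure's date and the earliest date consistent with the known month and year. The result must never contradict the known part or fall after a known stop date. The stop-date limit matters under this rule because the reporting contact can point to an exposure that came after the event had ended.

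State also that per-vaccination and per-phase tables use the assigned exposure. The cost is one SAP paragraph and a small programming change, with no new data. It should be settled before unblinding, so that events are not attributed to exposures case by case. A listing of partially dated events with assigned exposure and imputed date would show how many there are.
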